9.5. Electrocardiograms

[figure not shown]
The number and percentage of subjects with normal, abnormal not clinically significant, and abnormal clinically significant ECG results will be summarized by treatment group and by visit.

If applicable (digital ECGs), descriptive summaries will be presented by treatment group, visit and time point (for Day 1 only) for ECG measures of PR, QRS, QT, RR intervals and for the calculated variables QTcF and HR for each treatment group and time point.

Heart rate (HR) and Fridericia's correction (QTcF) will be derived as follows:

AD-ST-33.06 Effective date: 12-Nov-2020

Version 1.1 | Date 31-Aug-2023 | AD-PR-109.02 Effective date: 17-Aug-2020

Heart Rate (HR)
$$HR = 10^{3} \frac{60}{RR_{msec}}$$
Fridericia's Correction
$$QTc_{f} = \frac{QT_{msec}}{\sqrt[3]{RR}}$$
(QTcF)

9.6. Physical and Neurological Examination

The physical and neurological examination findings will be presented in listings.

9.7. Total Neuropathy Score-Nurse

Descriptive summaries of the TNSn will be presented by treatment groups and by visit. Additionally, the number and percentage of subjects within each category (0, 1, 2, 3, and 4) for each sub-score (sensory symptom, motor symptom, autonomic symptom, pin sensibility, vibration sensibility) will be summarized by treatment group and by visit.

9.8. Motor and Sensory Nerve Conduction Studies

Amplitude, peak latency, conduction velocity, and duration of nerve action potentials will be summarized by treatment group and visit for each location and evaluation type. The number of subjects with normal and abnormal evaluation will be tabulated by treatment group and by visit.

9.9. Strength and Deep Tendon Reflexes

The number and percentage of subjects within each category of the ankle dorsiflexion strength and the deep tendon reflexes will be tabulated by treatment group and by visit.

9.10. Hypersensitivity/Anaphylactic Reactions, Injection Site or Infusion Reactions

The type and symptoms of hypersensitivity/ anaphylactic reactions will be tabulated by treatment group.

Injection site reactions will be tabulated describing the severity of pain, tenderness, erythema/redness, and induration/swelling by treatment group and by visit.

[figure not shown]
Anaphylactic reactions and infusion related reactions will be summarized in line with AEs, displayed by treatment group and by:

- SOC and PT
- SOC, PT, and maximum severity (mild, moderate, severe)

Hypersensitivity/anaphylactic and infusion related reactions will also be presented in a by-

AD-ST-33.06 Effective date: 12-Nov-2020

Version 1.1 | Date 31-Aug-2023 | AD-PR-109.02 Effective date: 17-Aug-2020 Page 35 of 54

treatment and by-subject listings, detailing type of reaction, severity grade for symptom with highest severity and onset time for hypersensitivity/anaphylactic reactions, and assessment result for injection site or infusion related reactions.

9.11. Prior and Concomitant Medication and Procedures

Prior medications will be presented separately from concomitant medications.

Medications will be coded using the latest version of the WHO Drug Dictionary.

Medications that started before first dose of study medication will be considered prior, whether they were stopped before first dose of study medication or not.

A concomitant medication is defined as any medication continuing or starting after first dose of study medication. This includes medications which start before first dose of study medication and continue while on-treatment, and medications that started after first dose of study medication.

The frequency and percentage of concomitant medications will be summarized by Anatomical Therapeutic Chemical (ATC) class 2 and preferred name by treatment groups, unless otherwise specified.

In listings, all medications will be displayed.

[figure not shown]
If the start/stop dates of a medication are partially or completely missing, then the medication will be assumed to be concomitant if it cannot be definitely shown from the start/stop dates that it was not administered while on-treatment (from first exposure to treatment till last dose of study medication + 14 exposure days). Missing dates will not be replaced.

Thus, the following approach will be taken for exclusion from concomitant medications because of discontinuation before start of treatment:

- If the stop day is missing but the month is complete, then the medication will be excluded from concomitant medications only if the stop month is before the month of the first dose of study medication.
- If the stop day and month are missing but the year is complete, then the medication will be excluded from concomitant medications only if the stop year is before the year of the first dose of study medication.
- If the stop date is completely missing, then the medication will not be excluded.

For concomitant medication exclusion (because of the late start after the end of the treatment period):

• If the start day is missing but the month is complete, then the medication will be excluded from concomitant medications only if the start month is after the last month of the treatment period.

- If the start day and month are missing but the year is complete, then the medication will be excluded from concomitant medications only if the start year is after the year of the treatment period.
- If the start date is completely missing, then the medication will not be excluded.

A similar approach will be used for summarizing concomitant procedures.

10. Changes from Planned Analysis

The PK endpoints involving derivation of PK parameters for each dose and for each subject will be conducted by a population PK analysis of the data as part of a pooled data analysis instead of by a noncompartmental analysis (NCA). This will be documented in the CSR as a change in planned analysis. The pooled data analysis will be described in a separate modelling analysis plan. As a result, description of TLFs related to PK parameters are removed from this SAP.

Additional analyses with pooled site as a covariate are not going to be conducted and as such, they are removed from this SAP.

It was planned to have a supplementary analysis to the primary using an adaptive MCP-MOD method. In this analysis, stages 2+3 and stage 4 were going to be analysed separately and the results combined using an inverse-normal *P* value combination function (with weights related to the original planned sample sizes). This supplementary analysis is removed from this SAP.

The Cochran-Mantel-Haenszel test for the non-binary categorical endpoints has been extended to include the secondary endpoint of pain response.

The definition of TEAE from the protocol has been changed in this SAP, eliminating the condition for the AE onset not being more than 30 days after the last administration of IP to be regarded as a TEAE. The change in the definition of TEAE has been made upon Sponsor request, to enable transparency, adequate safety reporting and oversight of safety profile/risks.

[figure not shown]
11. Other Planned Analysis

11.1. **CC**

AD-ST-33.06 Effective date: 12-Nov-2020

Version 1.1 | Date 31-Aug-2023 | AD-PR-109.02 Effective date: 17-Aug-2020 Page 37 of 54

CCI		
CCI		
COI		

11.2. Immunogenicity

Blood samples will be collected for assessment of ADA levels. Anti-Drug Antibody response during the entire study period and at each study assessment will be summarised according to ADA category and titre value for the Safety population with evaluable ADA results. A listing of the ADA test results will be produced.

[figure not shown]
For immunogenicity analysis, the presence of detectable (i.e., positive) ADAs against MEDI7352 will be reported. ADA results from each sample are reported as either positive or negative. In addition, the ADA titer result will be reported for samples confirmed positive for the presence of ADAs. A participant is defined as being ADA-positive if a positive ADA result is available at any time, including baseline and all post-baseline measurements, otherwise ADA negative.

The following ADA categories will be determined:

- ADA positive if a collected sample is tested positive at any time during the study, including baseline and/or post-baseline. (The percentage of these participants in a population is known as ADA prevalence).
- Treatment-emergent ADA positive (TE-ADA+): A positive post-baseline result and either of the following statements holds:
 - Baseline is ADA negative and at least one post-baseline assessment is ADA positive. This is called treatment-induced ADA positive.
 - o Baseline is ADA positive, and the baseline titre is boosted by greater than the variability of the assay (i.e., ≥X-fold increase, commonly 4-fold) at ≥1 post-baseline timepoint. This is called treatment-boosted ADA positive.

(The percentage of these participants in a population is known as ADA incidence)

- Only baseline positive if a collected sample is tested positive at baseline.
- Non-Treatment-emergent ADA positive (non-TE-ADA+): Participants who are ADA positive but not fulfilling the conditions for TE-ADA+.
- Treatment-emergent Persistently ADA positive: ADA negative at baseline and having at least 2 post-baseline ADA positive measurements with ≥16 weeks (112 days) between first and last positive, or an ADA positive result at the last available post-baseline assessment.
- Treatment-emergent Transiently ADA positive: ADA negative at baseline and at least one post-baseline ADA positive measurement and not fulfilling the conditions for persistently positive

[figure not shown]
• ADA positive post-baseline and positive at baseline.

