4 PK AND IMMUNOGENICITY ASSESSMENTS

Blood samples for determination of serum MEDI7352 concentrations and serum total NGF concentrations are collected at the following time-points:

Day 1 (pre-treatment), Day 14, Day 28, Day 42, Day 56, Day 70 (pre-dose, end of infusion, and 8 h), Day 71, Day 77, Day 84 and Early termination (if relevant).

Blood samples for determination of presence of anti MEDI7352 antibodies (ADA) are collected at the following time-points:

Baseline, Day 14, Day 28, Day 56, Day 70, Day 84 and Week 18.

Note: on dosing days, blood samples are taken prior to IP administration.

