9.1. Adverse Events

A summary table by treatment group will present the number and percent of subjects reporting:

- Any AEs
- Non-serious AEs occurring in more than 5% of subjects
- Any TEAEs
- Any SAEs
- Any TEAEs possibley related to study drug
- Any TEAEs leading to discontinuation of IP
- Any SAEs possibley related to study drug
- Life-threatenings SAEs
- SAEs resulting in death

Summaries of the incidence of TEAEs will be displayed by treatment group, by ADA status, by severity and by:

- SOC and PT
- SOC, PT, and maximum severity (mild, moderate, severe)
- SOC, PT, and maximum causality (not related, possibly related) to the study drug

[figure not shown]
In the summaries showing severity and relationship to study drug the event with the maximum severity or strongest relationship will be reported. If a particular event is missing the severity and/or relationship, then the strongest possible severity or relationship will be assumed for analysis (severity = severe, relationship = related).

In the case of multiple occurrences of the same AE within the same subject, each subject will only be counted once for each level of summarization.

All AEs will be presented in a by-treatment and by-subject listing, detailing the verbatim term given by the Investigator, the PT, SOC, onset date and time, end date and time, severity, outcome, relationship to study drug, action taken with study drug, other action taken, seriousness, and criteria for seriousness.

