Reference Listing: 16.2.9.1

Programming Notes:

- Same shell as Figure 14.2.1.4
- Insert the following text as legend: "Average Body T° ± Standard Deviation".
- Study Visit in x axis and Body Temperature (°C) in y axis.
- Include the following timepoints: Baseline, Day 1: 1 hour Post-Dose, Day 1: 2 hours Post-Dose, Day 1: 4 hours Post-Dose, Week 2: Pre-Dose, Week 2: 5 minutes after Infusion Completion, Week 4: Pre-Dose, Week 4: 5 minutes after Infusion Completion, Week 6: Pre-Dose, Week 6: 5 minutes after Infusion Completion, Week 8: Pre-Dose, Week 8: 5 minutes after Infusion Completion, Week 10: Pre-Dose, Week 10: 5 minutes after Infusion Completion, Week 10: 4 hours, Week 11, Week 12, Week 18. (Do not include Screening records).
- Make one plot with 4 profiles (one for each treatment group).
- A plot for column dosing column dosing column will only be added if Stage 4 is initiated.

Final 1.0 | 12-Jul-2023 | Page 199 of 205

[figure not shown]
[figure not shown]

Figure 14.4.1.1

Pharmacokinetics: Line Plot of Geometric Mean (with and without gSD) Serum MEDI7352 Concentrations over time PK Population

ADA = Antidrug Antibodies; gMean = Geometric Mean.

[figure not shown]
PK Population = includes all subjects for who a pharmacokinetic sample was obtained and analyzed.

ADA positive represents number of participants with at least one positive ADA result.

ADA negative represents number of participants with only negative ADA results (no positive).

Reference Listing: 16.2.10.1

Final 1.0 | 12-Jul-2023 | Page 200 of 205

Programming Notes:

- Insert the following text as upper legend: "Geometric Mean serum MEDI7352 ± Geometric Standard Deviation" for the linear plot, and "Geometric Mean serum MEDI7352" for the semi-log plot. Below legend, add legend for ADA status: "Overall", "ADA Positive", "ADA Negative".
- Insert legend with different point symbols and colors for each treatment group (CC) for the Overall plot, and a legend with different point symbols and colors for each ADA status (ADA+, ADA-) for each treatment group plot by ADA status.
- Study Visit in x axis and Serum MEDI7352 concentration (ng/mL) in y axis (in linear and log₁₀ scale, for each plot).
- Include data from the following timepoints: Baseline (Day 1), Week 2, Week 4, Week 6, Week 8, Week 10: Pre-Dose, Week 10: Before End of Infusion, Week 10: 8 Hours after Infusion, Week 10 + 24 hours, Week 11, Week 10 + 14 days, Week 18.

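### ADA status needs no post-baseline result and 'persistent' reduces to a positive last available sample, so early withdrawal helps to decide the ADA category

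*SAP*

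**What the plan says.** **Participant-level status.** SAP v1.1 section 11.2 (same text in v1.0) reads: "A participant is defined as being ADA-positive if a positive ADA result is available at any time, including baseline and all post-baseline measurements, otherwise ADA". The sentence ends by making everyone else negative. The ADA summary is "for the Safety population with evaluable ADA results"; what makes a result evaluable is not defined.

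**Persistence.** A baseline-negative subject can be treatment-emergent persistently positive in two ways. The first limb asks for "at least 2 post-baseline ADA positive measurements with ≥16 weeks (112 days) between first and last positive". The second limb, as an alternative, reads "or an ADA positive result at the last available post-baseline assessment". A baseline-negative subject with at least one post-baseline positive who meets neither limb is transient.

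**Where the categories are used.** Section 9.1: "Summaries of the incidence of TEAEs will be displayed by treatment group, by ADA status, by severity and by" coding level. The shell for Table 14.3.1.5 refers back to the SAP for its categories. It has eight columns, none for subjects who cannot be classified, and its denominator is the number of subjects in each category.

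**Denominators.** The shell for Table 14.3.5.20 uses any ADA result for prevalence (Nobs note 2). For incidence, persistent and transient ADA it uses a baseline result plus at least one post-baseline assessment (Nobs note 3). A programming note under the same table treats a missing baseline as negative.

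**Sampling.** Section 4 of the interim plan lists ADA samples at "Baseline, Day 14, Day 28, Day 56, Day 70, Day 84 and Week 18". The shell for Listing 16.2.9.19 has the same visits. The interim plan names an early-termination sample for PK and NGF but not for ADA.

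The shells for these outputs are those of v1.0; the v1.1 shells at hand stop before them.

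**The concern.** Two features let follow-up time decide the ADA label.

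First, a subject who was never tested after dosing is grouped with subjects who were tested and found negative. The ADA Negative column of Table 14.3.1.5 is the natural comparator for adverse events in ADA-positive subjects. It would mix tested negatives with early leavers whose treatment-emergent status is unknown. Subjects who stop early may well differ in their adverse events, so the mixture need not be neutral.

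Second, 'persistent' suggests a response shown to last. If a single positive sample before withdrawal is enough, the persistent and transient rates partly measure dropout, and arms with different withdrawal would differ in these rates for that reason alone. Both categories are also columns in Table 14.3.1.5.

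**Working it through.** **1. The plan's own interval.** 16 × 7 = 112 days, as stated.

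**2. Subjects with no post-baseline ADA result under section 11.2**

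| Baseline ADA | Status | Prevalence denominator (Nobs 2) | Incidence, persistent and transient denominator (Nobs 3) |
|---|---|---|---|
| Negative | ADA negative | in | out |
| Positive | ADA positive | in | out |
| No result | ADA negative by default | out | out |

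The footnote to the Figure 14.4.1.1 shell ("ADA negative represents number of participants with only negative ADA results (no positive") does not exclude the first row, since a single negative baseline satisfies it.

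**3. Size for prevalence.** Planned numbers for stages 2 to 4 (section 3.2): 30 + 67 + 165 = 262 randomised and 28 + 60 + 148 = 236 evaluable. The difference is 26, and 26/262 = 9.9%, which reproduces the stated 10%. Assume no baseline positives and let m subjects have a baseline but no post-baseline ADA result. Reported prevalence = true prevalence × (262 − m)/262.

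| True prevalence | m = 0 | m = 13 | m = 26 |
|---|---|---|---|
| 10% | 10.0% | 9.5% | 9.0% |
| 20% | 20.0% | 19.0% | 18.0% |
| 40% | 40.0% | 38.0% | 36.0% |

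On planned numbers m = 26 is an upper bound, because some subjects not evaluable for pain will still have a Day 14 ADA sample. Incidence does not move.

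**4. The 16-week limb.** Post-baseline sample days are 14, 28, 56, 70, 84 and 126 (Week 18).

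- Longest span: 126 − 14 = 112 days. Next longest: 126 − 28 = 98 days. Longest without Week 18: 84 − 14 = 70 days.
- A pair 112 days apart therefore has to end at Week 18, the last scheduled sample. Visit windows of a few days do not change this.

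For a baseline-negative subject whose last sample is the k-th of six, there are 2^k − 1 result patterns with at least one positive:

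- All patterns: 1 + 3 + 7 + 15 + 31 + 63 = 120.
- Last available sample positive: 1 + 2 + 4 + 8 + 16 + 32 = 63.
- 16-week limb met (Day 14 and Day 126 both positive, the four samples between free): 2^4 = 16.
- 16-week limb met without the last-sample limb: 0.

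So 'persistent' coincides with 'last available sample positive'. These are counts of possible patterns, not probabilities.

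**5. Single positives.** A subject whose only positive is the last sample is persistent at all six possible last-sample days, five of which are exits before Week 18. The same subject who stays and tests negative at Week 18 is transient.

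**The case against.** The strongest reply is that the plan already handles much of this. Nobs note 3 keeps subjects without a post-baseline assessment out of the incidence, persistent and transient percentages, and the by-visit ADA table counts only subjects with a result at that visit. That stands. It confines the first part to the binary label in Table 14.3.1.5 and the prevalence denominator.

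Three stronger readings are tempting and not supported:

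- *The PK and NGF comparisons by ADA status are biased.* PK, NGF and ADA share Day 14 as the first post-baseline visit. A subject gone before then contributes essentially a pre-dose value, and the shell timepoint lists have no early-termination entry. These outputs split on positive and negative only, so the persistence rule cannot reach them. The effect is negligible.
- *First-infusion reactors are misclassified as negative.* Treatment-induced ADA cannot explain a reaction to the first exposure, and the baseline sample tests for pre-existing ADA. A baseline-positive early leaver counts as ADA positive. This is a weak example of harm.
- *A real ADA-versus-AE contrast disappears.* Take 68 tested negatives with a 2% event rate (1.36 expected events) and add five untested early leavers. If all five had the event, the rate is (1.36 + 5)/73 = 8.7%; if none did, it is 1.36/73 = 1.9%. Every input is assumed, so this shows only that the direction and size depend on who leaves.

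The protocol's schedule was not available for this check and may include an early-termination ADA sample. That would reduce the number affected without repairing the definition.

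It is also fair that the last-sample rule is explicit and reproducible, that the redundant 16-week limb reclassifies nobody, and that Listing 16.2.9.19 shows every sample by day. A listing does not correct the summary tables, however.

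**Conclusion.** The point holds within limits. Section 11.2 assigns ADA negative to any subject without a positive result, including those never sampled after dosing, and Table 14.3.1.5 has nowhere else to put them. For prevalence the understatement is at most about one tenth of the true value (20% shown as 18%), assuming that all 26 planned non-evaluable subjects lack a post-baseline result and that nobody is positive at baseline. For the ADA Negative column of Table 14.3.1.5 the documents give no basis for a figure.

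On the listed schedule, persistent ADA means that the last available sample was positive. One positive followed by withdrawal qualifies, and the persistent and transient rates therefore depend on dropout. This rests on the sampling days in the interim plan, which agree with the listing shell.

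Section 9 makes the safety analyses descriptive, without inferential tests. No efficacy result, alpha or power figure is affected. The change is worthwhile because the plan already applies the right principle in one table and not in the other.

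**What to change.** - In section 11.2, define ADA negative as no positive result and at least one post-baseline ADA result.
- In Table 14.3.1.5, add an 'ADA not evaluable' column for dosed subjects with no positive result and no post-baseline result.
- Carry the Nobs note 3 denominator of Table 14.3.5.20 into section 11.2, and reconcile it with the note that treats a missing baseline as negative. As written, a subject can be classified as baseline negative for the numerator and yet be absent from a denominator that requires a baseline result.
- In Table 14.3.5.20, report baseline-negative subjects who are positive at their last sample but have no Week 18 result in a separate row, 'positive at last sample, follow-up incomplete', outside the persistent group.
- State that the 16-week clause adds no one under this schedule.

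This does not alter every awkward case. A subject positive at all five samples from Day 14 to Day 84 and negative at Week 18 remains transient.

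The cost is SAP wording, one column and one row, with no new data. The downside is slightly smaller ADA-negative and persistent groups.

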13.1. Demographic Data

Table 1: Demographic Data Summary Tables and Figures

Table Number	Population	Table Title/Summary
Table 14.1.2	Screening	Subject Disposition
Table 14.1.3	Screen Failure	Summary of Reasons for Screening Failure
Table 14.1.4.1	Screening	Demographics and Baseline Characteristics
Table 14.1.4.2	Safety	Demographics and Baseline Characteristics
Table 14.1.4.3	mITT	Demographics and Baseline Characteristics
Table 14.1.4.4	PK	Demographics and Baseline Characteristics
Table 14.1.5.1	Screening	Osteoarthritis Characteristics
Table 14.1.5.2	Safety	Osteoarthritis Characteristics
Table 14.1.5.3	mITT	Osteoarthritis Characteristics
Table 14.1.5.4	PK	Osteoarthritis Characteristics
Table 14.1.6	Safety	Medical History by System Organ Class and Preferred Term
Table 14.1.7	Safety	Prior Medications by ATC Class and Preferred Name
Table 14.1.8	Safety	Protocol Deviations
Table 14.1.9	Safety	Overall Study Drug Exposure

117 of 762

AD-ST-33.06 Effective date: 12-Nov-2020

Version 1.1 | Date 31-Aug-2023 | AD-PR-109.02 Effective date: 17-Aug-2020

[figure not shown]
